#### 6.1.4 Trametinib and/or GSK2141795 Dose Modification for Diarrhea

Episodes of diarrhea have occurred in patients receiving trametinib or GSK2141795 (Investigator’s Brochure, 2012a). Other frequent causes of diarrhea may include concomitant medications (*e.g.*, stool softeners, laxatives, antacids, *etc.*), infections by *C. difficile* or other pathogens, or partial bowel obstruction. Those conditions should be excluded.

Guidelines regarding management and dose modification for diarrhea considered related to trametinib and/or GSK2141795 are provided in the table below.

Management and Study Drug(s) Modification Guidelines for Diarrhea		
CTCAE Grade	Adverse Event Management	Action and Dose Modification
Uncomplicated Diarrhea, Grade 1 or 2	
 
• Diet: Stop all lactose containing products; eat small meals, BRAT-diet (bananas, rice, apples, toast) recommended.
 
• Hydration: 8-10 large glasses of clear liquids per day (e.g., Gatorade or broth).
 
• Loperamide: Initially 4 mg, followed by 2 mg every 4 hours or after every unformed stool; maximum 16 mg/day. Continue until diarrhea-free for 12 hours.
 
• Diarrhea >24 hours: Loperamide 2 mg every 2 hours; maximum 16 mg/day. Consider adding oral antibiotics.
 
• Diarrhea >48 h: Loperamide 2 mg every 2 hours; maximum 16 mg/day. Add budesonide or other second-line therapies (otretotide, or tincture of opium) and oral antibiotics.
 
	
 
• Continue study drug(s).
 
• If diarrhea is grade 2 for > 48 h, interrupt study drug(s) until diarrhea resolves to grade ≤1.
 
• Restart study drug(s) at the same dose level
 
• If treatment delay is ≥28 days, discontinue study drug(s).
 

**Management and Study Drug(s) Modification Guidelines for Diarrhea**

CTCAE Grade	Adverse Event Management	Action and Dose Modification

Uncomplicated Diarrhea, Grade 3 or 4
 
Any Complicated Diarrhea
	
 
• Clinical evaluation mandatory.
 
• Loperamide: Initially 4 mg, followed by 2 mg every 4 hours or after every unformed stool; maximum 16 mg/day. Continue until diarrhea-free for 12 hours.
 
• Oral antibiotics and second-line therapies if clinically indicated
 
• Hydration: Intravenous fluids if clinically indicated.
 
• Antibiotics (oral or intravenous) if clinically indicated.
 
• Intervention should be continued until the subject is diarrhea-free for <math>\geq 24</math> hours.
 
• Intervention may require hospitalization for subjects at risk of life-threatening complications.
 
	
 
• Interrupt study drug(s) until diarrhea resolves to <math>\leq</math> grade 1.
 
• Restart with study drug(s) reduced by one dose level.
 
• If 3 dose reductions of study treatment are clinically indicated, permanently discontinue study drug(s).
 
• If treatment delay is <math>\geq 28</math> days, discontinue study drug(s).
 

1. Uncomplicated diarrhea defined by the absence of symptoms such as cramping, nausea/vomiting, <math>\geq</math> grade 2, decreased performance status, pyrexia, sepsis, neutropenia <math>\geq</math> grade 3, frank bleeding, and/or dehydration requiring intravenous fluid substitution.
 
2. Complicated diarrhea defined by the presence of symptoms such as cramping, nausea/vomiting, <math>\geq</math> grade 2, decreased performance status, pyrexia, sepsis, neutropenia <math>\geq</math> grade 3, frank bleeding, and/or dehydration requiring intravenous fluid substitution.
 
3. Loperamide should be made available prior to start of study treatment so loperamide administration can begin at the first signs of diarrhea.
 
4. Escalation of trametinib to previous dose level is allowed after consultation with the medical monitor and in the absence of another episode of complicated or severe diarrhea in the 4 weeks subsequent to dose reduction.
		

6.1.5 Trametinib and/or GSK2141795 Dose Modification for Liver Chemistry Changes

Study Drug(s) Dose Modification for Liver Function Test Abnormalities	
Event	Treatment modifications and assessment/monitoring

 
• ALT <math>\geq 3x</math> ULN but <math>< 5x</math> ULN and TB <math>< 2x</math> ULN, without symptoms considered related to liver injury or hypersensitivity and who can be monitored weekly for 4 weeks
 
	
 
• May continue study drug.
 
• Report as SAE if CTEP-AERS reporting criteria is met.
 
• If liver chemistry stopping criteria are met any time, proceed as described below.
 
 
MONITORING: Repeat LFT (ALT, AST, ALK, bilirubin) until they return to normal/baseline or stabilise (LFT may be every 2 weeks after 4 weeks if ALT <math>< 3x</math> ULN and TB <math>< 2</math> ULN).


Criteria for discontinuing study drug: When any of the liver stopping criteria below is met, discontinue trametinib
 
 
1) ALT <math>\geq 3x</math> ULN and bilirubin <math>\geq 2x</math> ULN or <math>> 35\%</math> direct bilirubin
 
2) ALT <math>\geq 3x</math> ULN and INR <math>> 1.5</math>, if INR measured (INR threshold does not apply if subject is on anticoagulant)
 
3) ALT <math>\geq 5x</math> ULN
 
4) ALT <math>\geq 3x</math> ULN persists for <math>\geq 4</math> weeks
 
5) ALT <math>\geq 3x</math> ULN and cannot be monitored weekly for 4 weeks
 
6) ALT <math>\geq 3x</math> ULN associated with symptoms (new or worsening) believed to be related to liver injury or hypersensitivity
 
	
Immediately discontinue study treatment.
 
 
• Do not restart/rechallenge unless approved by CTEP trametinib medical monitor. [
 
• Report as SAE if: 1) CTEP-AERS reporting criteria are met, or 2) patients meet criteria 1-2.
 
• Perform liver event ASSESSMENT AND WORKUP (see below).
 
• Monitor the subject until liver chemistries resolve, stabilize, or return to baseline (see MONITORING below).
 
 
MONITORING: In patients stopping for criteria 1-2 (with abnormal TB and INR, indicating potentially more significant liver toxicities):
 
 
• Repeat liver chemistries (ALT, AST, ALK, bilirubin) and perform liver event follow-up assessments within 24 hours.
 
• Monitor subjects twice weekly until LFT return to normal/baseline or stabilize.
 
• A special list or hepatology consultation is recommended.
 
 
In patients stopping for criteria 2-6:
 
 
• Repeat LFT and perform liver event follow up assessments within 24-72 hrs
 
• Monitor subjects weekly until LFTs return to normal/baseline or stabilize.
 
 
ASSESSMENT and WORKUP:
 
 
• Viral hepatitis serology.
 
• Serum CPK and LDH.
 
• Fractionate bilirubin, if total bilirubin <math>\geq 2x</math> ULN.
 
• CBC with differential to assess eosinophilia.
 
• Record clinical symptoms of liver injury, or hypersensitivity on AE CRF.
 
• Record concomitant medications (including a cetaminophen, herbal remedies, other over the counter medications).
 
• Record alcohol use.
 
 
Additional work up for patient stopping for criteria 1-2 (with abnormal TB and INR, indicating potentially more significant liver toxicities):

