  - Total bilirubin  $\leq 1.5 \times$  institutional ULN (isolated bilirubin  $> 1.5 \times$  ULN is acceptable if bilirubin is fractionated and direct bilirubin  $< 35\%$ )
  - Aspartate aminotransferase (AST) and alanine aminotransferase (ALT)  $\leq 2.5 \times$  institutional ULN

- Serum creatinine  $\leq 1.5$  mg/dL *OR* calculated creatinine clearance (Cockcroft-Gault formula)  $\geq 30$  mL/min *OR* 24-hour urine creatinine clearance  $\geq 30$  mL/min
- Prothrombin time (PT)/International normalized ratio (INR) and partial thromboplastin time (PTT)  $\leq 1.5$ x institutional ULN
- Fasting serum glucose  $< 126$  mg/dl (7 mmol/l)
- Left ventricular ejection fraction (LVEF)  $\geq$  institutional lower limit of normal (LLN) by ECHO or MUGA

3.1.11 Subjects that have been previously diagnosed with Type 2 diabetes or steroid-induced diabetes must also meet the additional following criteria:

- Diagnosed with diabetes  $\geq 6$  months prior to enrolment
- HbA1C  $\leq 8\%$  at screening visit

3.1.12 The effects of trametinib *or* GSK2141795 on the developing human fetus are unknown. For this reason and because MEK inhibitors as well as other therapeutic agents used are known to be teratogenic, women of child-bearing potential and men must agree to use adequate contraception (hormonal or barrier method of birth control; abstinence) prior to study entry and for the duration of study participation. Women of child-bearing potential must have a negative serum pregnancy test within 7 days prior to the start of protocol therapy. Should a woman become pregnant or suspect she is pregnant while she or her partner is participating in this study, she should inform her treating physician immediately. Men treated or enrolled on this protocol must also agree to use adequate contraception prior to the study, for the duration of study participation, and 4 months after completion of trametinib administration.

3.1.13 Ability to understand and the willingness to sign a written informed consent document.

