
**Study Drug(s) Dose Modification for Liver Function Test Abnormalities**

Event	Treatment modifications and assessment/monitoring
	
 
• Anti-nuclear antibody, anti-smooth muscle antibody, Type 1 anti-liver kidney microsomal antibodies, and quantitative total immunoglobulin G (IgG or gamma globulins).
 
• Serum acetaminophen adduct HPLC assay (in subjects with likely acetaminophen use in the preceding).
 
• If there is underlying chronic hepatitis B (e.g. positive hepatitis B surface antigen): quantitative hepatitis B DNA and hepatitis delta antibody.
 
• Liver imaging (ultrasound, MRI, CT) and /or liver biopsy.
 

Footnotes:
 
1. Serum bilirubin fractionation should be performed if testing is available. If serum bilirubin fractionation testing is unavailable, record presence of detectable urinary bilirubin on dipstick, which indicates direct bilirubin elevations and suggesting liver injury.
 
2. All events of ALT <math>\geq 3 \times</math> ULN and bilirubin <math>\geq 2 \times</math> ULN (>35% direct bilirubin) or ALT <math>\geq 3 \times</math> ULN and INR >1.5 (if INR measured) may indicate severe liver injury (possible “Hy’s Law”). INR measurement is not required, and the threshold value stated will not apply to subjects receiving anticoagulants.
 
3. New or worsening symptoms believed to be related to liver injury (such as fatigue, nausea, vomiting, right upper quadrant pain or tenderness, or jaundice) or believed to be related to hypersensitivity (such as fever, rash or eosinophilia)
 
4. Includes: Hepatitis A IgM antibody; Hepatitis B surface antigen and Hepatitis B Core Antibody (IgM); Hepatitis C RNA; Cytomegalovirus IgM antibody; Epstein-Barr viral capsid antigen IgM antibody (or if unavailable, obtain heterophile antibody or monospot testing); Hepatitis E IgM antibody
 
5. If hepatitis delta antibody assay cannot be performed, it can be replaced with a PCR of hepatitis D RNA virus (where needed) (Le Gal et al., 2005).
	

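### The liver stopping table in 6.1.5 is inconsistent on whether GSK2141795 stops along with trametinib, and on whether direct bilirubin above 35% is an alternative or an added condition

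*Combined protocol and SAP*

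**What the plan says.** **Which drug stops.** Section 6.1.5 is headed "Trametinib and/or GSK2141795 Dose Modification for Liver Chemistry Changes", and its table title refers to the study drug(s). In the stopping row, the event cell introduces the six criteria with "When any of the liver stopping criteria below is met, discontinue trametinib". The action cell of the same row says "Immediately discontinue study treatment". On restarting, it says "Do not restart/rechallenge unless approved by CTEP trametinib medical monitor"; no monitor for GSK2141795 is named.

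**Direct bilirubin.** Criterion 1 requires ALT of at least 3x ULN together with a bilirubin condition that ends "ULN or > 35\% direct bilirubin". Footnote 2, attached to that criterion, describes the event with the direct fraction in brackets after the 2x threshold: "ULN (>35% direct bilirubin) or ALT".

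Four other places bear on this:
- The work-up list says "Fractionate bilirubin, if total bilirubin" is at least 2x ULN.
- Footnote 1 asks for fractionation whenever the test is available, with no threshold.
- Row 1 lets a patient continue at ALT 3 to <5x ULN with total bilirubin below 2x ULN if there are no liver or hypersensitivity symptoms and weekly monitoring is possible. It does not mention direct bilirubin, and it gives way if a stopping criterion is met.
- Eligibility criterion 3.1.10 admits a patient with isolated bilirubin above 1.5x ULN, which "is acceptable if bilirubin is fractionated and direct bilirubin" is below 35%.

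Meeting criterion 1 or 2 also requires an SAE report.

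**The concern.** This is an operative safety rule, and sites acting in good faith could apply it differently.

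For a patient on the combination, a site that follows the event cell has no order to stop GSK2141795; a site that follows the action cell stops it. The second drug's liver profile makes this relevant. Section 2.2.1.5 lists AST and ALT elevation among the dose-limiting toxicities of the combination, with AST elevation in 22% (grade 3/4 in 9%). The GSK2141795 risk list in 7.1.1.2 includes raised transaminases and hepatic failure, with the relationship still undetermined.

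For bilirubin, the reading chosen decides whether some patients stop, whether an SAE is filed under criterion 1, and which monitoring schedule and work-up apply.

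**Working it through.** There is no stated figure to reproduce. The check compares wording and then enumerates the rule.

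**1. Are the two drug terms interchangeable?** The protocol does not use them so. Sections 6.1.6 (pneumonitis) and 6.1.7 (LVEF) concern trametinib and name it. Section 6.1.8 (QTc) covers both drugs and refers to study treatment. Section 6.1.1 leaves it to the investigator to judge which drug to adjust, but expressly excludes liver chemistry, so it does not settle the point. The event cell orders a stop of one drug and is silent on the other; the action cell stops both.

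**2. Enumerating criterion 1.** Inputs are row 1, criterion 1 and criterion 3 (ALT at least 5x ULN). Criteria 2 and 4 to 6 are taken as not met. ALT of at least 3x ULN is taken to govern both bilirubin terms, and the 2x threshold to mean total bilirubin (TB).

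- *Or* reading: ALT at least 3x, and (TB at least 2x or direct above 35%).
- *And* reading: ALT at least 3x, and (TB at least 2x and direct above 35%).

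| ALT (x ULN) | TB (x ULN) | Direct | Row 1 fits | *Or* reading | *And* reading |
|---|---|---|---|---|---|
| 3 to <5 | <2 | ≤35% | yes | may continue | may continue |
| 3 to <5 | <2 | >35% | yes | stop, SAE report (row 1 gives way) | may continue |
| 3 to <5 | ≥2 | ≤35% | no | stop, SAE report | no instruction |
| 3 to <5 | ≥2 | >35% | no | stop, SAE report | stop, SAE report |
| ≥5 | any (4 patterns with direct) | | no | stop (criterion 3) | stop (criterion 3) |

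The stop decision differs in 2 of 8 patterns, both at ALT 3 to <5x ULN. At ALT of at least 5x the stop is the same either way, although membership of criterion 1 still decides its automatic SAE report and closer monitoring.

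**3. Can each pattern occur?** The third row of the table can arise from 3.1.10, which sets no upper limit on an isolated, mainly indirect bilirubin elevation; ALT then has to rise on treatment. The second row can be detected only if bilirubin is fractionated while total bilirubin is below 2x ULN. Footnote 1 would prompt that where testing is available. The work-up line would not, and the study calendar's chemistry panel lists total bilirubin only.

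**4. Which reading does the surrounding text favour?** It is mixed. The work-up and monitoring text describes criteria 1 and 2 as having abnormal total bilirubin and INR, and the fractionation line uses the 2x threshold; both fit *and*. Criterion 1 itself and footnote 1 fit *or*.

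**The case against.** The strongest reply is that the table can be followed safely as it stands. The action column is where orders belong, it says to stop study treatment, and obeying it satisfies both cells. The event cell is itself headed as criteria for discontinuing study drug. Criterion 1 is the only operative bilirubin rule: footnote 2 describes possible Hy's law events and orders nothing. The work-up list is carried out after a criterion is met, so it does not define one.

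Much of this stands, and it rules out several stronger readings that a reader might infer:

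- *That the table orders GSK2141795 to continue.* It does not. The event cell is silent, and nothing says trametinib only.
- *That a patient with isolated indirect hyperbilirubinaemia gets opposite instructions.* Under *or* the patient stops. Under *and* criterion 1 is not met, but row 1 requires total bilirubin below 2x ULN and so cannot apply. The result is a gap, not an order to continue.
- *That the stop is permanent.* Restart is possible with approval, and the protocol says so explicitly elsewhere when it means permanent discontinuation.
- *That the liver-test rates in 2.2.1.3 size the problem.* They come from 2 mg monotherapy, where the drug conflict cannot arise, and they count any liver-test abnormality, not the two patterns above.
- *That the primary analysis is damaged.* Both cells stop trametinib, and 13.5.2 keeps eligible patients in the response analysis despite incorrect drug administration.

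What does not stand is that no repair is needed. A footnote attached to a criterion will be read as explaining it, and a site that relies on the event cell alone has no instruction to stop the second drug.

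**Conclusion.** Wrong as written, in two respects. First, one row under a two-drug heading differs between its cells on whether GSK2141795 stops. Second, criterion 1 and its footnote differ on whether direct bilirubin above 35% is an alternative or an added condition, and the two fractionation instructions do not resolve this.

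The true reversal, stop versus may continue, is confined to ALT 3 to <5x ULN with total bilirubin below 2x and direct above 35%. The pattern that 3.1.10 can admit yields stop versus no instruction. This rests on the assumptions listed with the enumeration, and on reading the brackets in footnote 2 as a joint condition.

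The documents do not say how many patients would fall in either pattern, so no count is offered. Sample size, power and alpha are unaffected. The consequence is for patient safety and for consistent SAE reporting across sites.

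**What to change.** Reconcile the event and action cells so that the row names the same drug or drugs for a patient on the combination, and make the restart approval consistent with that. Reconcile criterion 1, row 1, footnotes 1 and 2 and the work-up's fractionation line to one bilirubin condition. Then test the result against the eight patterns above, including the patient admitted under 3.1.10, so that each pattern has exactly one instruction. Which drugs stop and which bilirubin condition applies are for the sponsor to decide; no position is taken here.

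The cost is wording in one table and its footnotes. No patients are added. Whether any extra bilirubin fractionation is needed depends on the condition chosen, since the calendar's panel lists total bilirubin only.

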
**Study Drug(s) Dose Modification for Liver Function Test Abnormalities**

Event	Treatment modifications and assessment/monitoring
	
 
• Anti-nuclear antibody, anti-smooth muscle antibody, Type 1 anti-liver kidney microsomal antibodies, and quantitative total immunoglobulin G (IgG or gamma globulins).
 
• Serum acetaminophen adduct HPLC assay (in subjects with likely acetaminophen use in the preceding).
 
• If there is underlying chronic hepatitis B (e.g. positive hepatitis B surface antigen): quantitative hepatitis B DNA and hepatitis delta antibody.
 
• Liver imaging (ultrasound, MRI, CT) and /or liver biopsy.
 

Footnotes:
 
1. Serum bilirubin fractionation should be performed if testing is available. If serum bilirubin fractionation testing is unavailable, record presence of detectable urinary bilirubin on dipstick, which indicates direct bilirubin elevations and suggesting liver injury.
 
2. All events of ALT <math>\geq 3 \times</math> ULN and bilirubin <math>\geq 2 \times</math> ULN (>35% direct bilirubin) or ALT <math>\geq 3 \times</math> ULN and INR >1.5 (if INR measured) may indicate severe liver injury (possible “Hy’s Law”). INR measurement is not required, and the threshold value stated will not apply to subjects receiving anticoagulants.
 
3. New or worsening symptoms believed to be related to liver injury (such as fatigue, nausea, vomiting, right upper quadrant pain or tenderness, or jaundice) or believed to be related to hypersensitivity (such as fever, rash or eosinophilia)
 
4. Includes: Hepatitis A IgM antibody; Hepatitis B surface antigen and Hepatitis B Core Antibody (IgM); Hepatitis C RNA; Cytomegalovirus IgM antibody; Epstein-Barr viral capsid antigen IgM antibody (or if unavailable, obtain heterophile antibody or monospot testing); Hepatitis E IgM antibody
 
5. If hepatitis delta antibody assay cannot be performed, it can be replaced with a PCR of hepatitis D RNA virus (where needed) (Le Gal et al., 2005).
	

### 6.1.6 Trametinib Dose Modification for Pneumonitis

Pneumonitis has been observed in patients receiving trametinib. To reduce the risk of pneumonitis, patients will be monitored closely for symptoms and evaluated with imaging and functional tests. Dose modification and supportive care guidelines for pneumonitis are described in the tables below.

Management and Study Drug Modification Guidelines for Pneumonitis		
CTCAE Grade	Adverse Event Management	Action and Dose Modification
Grade 1	
 
• CT scan (high-resolution with lung windows) recommended.
 
• Work-up for infection.
 
• Monitoring of oxygenation via pulse-oximetry recommended.
 
• Consultation with pulmonologist recommended.
 
	Continue trametinib at current dose.
Grade 2	
 
• CT scan (high-resolution with lung windows).
 
• Work-up for infection.
 
• Consult pulmonologist.
 
• Pulmonary function tests: If < normal, repeat every 8 weeks until <math>\geq</math> normal.
 
• Bronchoscopy with biopsy and/or BAL recommended.
 
• Symptomatic therapy including corticosteroids if clinically indicated.
 
	
 
• Interrupt trametinib until recovery to grade <math>\leq 1</math>.
 
• If AE resolved to grade <math>\leq 1</math> and relationship to trametinib is equivocal, restarting trametinib with one dose reduction may be considered, after discussion with the medical monitor.
 
• If treatment delay is <math>\geq 28</math> days, permanently discontinue trametinib.
 

Grade 3	
 
• CT scan (high-resolution with lung windows).
 
• Work-up for infection.
 
• Consult pulmonologist.
 
• Pulmonary function tests-if < normal, repeat every 8 weeks until <math>\geq</math> normal.
 
• Bronchoscopy with biopsy and/or BAL if possible.
 
• Symptomatic therapy including corticosteroids as clinically indicated.
 
	
 
• Interrupt trametinib until recovery to grade <math>\leq 1</math>.
 
• If AE resolved to grade <math>\leq 1</math> and relationship to trametinib is equivocal, restarting trametinib with one dose reduction may be considered, after discussion with the medical monitor.
 
• If treatment delay is <math>\geq 28</math> days, permanently discontinue trametinib.
 

Grade 4	Same as grade 3.	Permanently discontinue trametinib.

Abbreviations: BAL = bronchoalveolar lavage; CT = computed tomography.

### 6.1.7 Trametinib Dose Modification for Reduced Left Ventricular Ejection Fraction

Decreases of the left ventricular ejection fraction (LVEF) have been observed in patients receiving trametinib. Therefore, ECHOs must be performed in regular intervals outlined in the Study Calendar. The same procedure (either ECHO or MUGA, although ECHO is preferred) should be performed at baseline and at follow-up visit(s).

Trametinib Dose Modification Guidelines and Stopping Criteria for LVEF Decrease		
Clinic	LVEF-drop (%) or CTCAE grade	Action and Dose Modification
Asymptomatic	Absolute decrease of >10% in LVEF compared to baseline and ejection fraction below the institution's LLN.	
 
• Interrupt trametinib and repeat ECHO/MUGA within 2 weeks.a
 
• If the LVEF recovers within 4 weeks (defined as LVEF ≥ LLN and absolute decrease ≤ 10% compared to baseline):               
 
– Consult with the CTEP trametinib medical monitor and request approval for restart.
 
– Restart treatment with trametinib at reduced dose by one dose level.b
 
– Repeat ECHO/MUGA 2, 4, 8, and 12 weeks after re-start; continue in intervals of 12 weeks thereafter.
 
 
 
• If LVEF does not recover within 4 weeks:               
 
– Consult with cardiologist.
 
– Permanently discontinue trametinib.
 
– Report as SAE
 
– Repeat ECHO/MUGA after 2, 4, 8, 12, and 16 weeks or until resolution.
 
– Consult with the CTEP trametinib medical monitor.c
 
 
 

Symptomaticb	
 
• Grade 3: resting LVEF 39-20% or >20% absolute reduction from baseline
 
• Grade 4: Resting LVEF ≤ 20%.
 
	
 
• Permanently discontinue trametinib.
 
• Report as SAE.
 
• Consult with cardiologist.
 
• Repeat ECHO/MUGA after 2, 4, 8, 12, and 16 weeks or until resolution.
 

a If ECHO/MUGA does not show LVEF recovery after 2 weeks, repeat ECHO/MUGA 2 weeks later.  
b Escalation of trametinib to previous dose level can be considered if LVEF remains stable for 4 weeks after restarting of trametinib. Approval from the CTEP trametinib medical monitor is required.  
c Symptoms may include: dyspnea, orthopnea, and other signs and symptoms of pulmonary congestion and edema.

